## 9. Analysis Set

### 9.1. Evaluable Population for Analysis

Analysis will be carried out for the evaluable population. This is defined as those individuals who meet the eligibility criteria and complete at least one of the screening assessments (MRI, ultrasound or PSA).

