Comparison of different testing combinations in terms of biopsy rates, detection of clinically insignificant cancer and significant cancers	
 
Hypothetical diagnostic pathways (HDP) of the different testing combinations being analysed (Section 8.3): 
 
MRI
 
Ultrasound
 
PSA (<math>\geq 1.0\text{ng/ml}</math>) & MRI
 
PSA (<math>\geq 3.0\text{ng/ml}</math>) & MRI
 
PSA & ultrasound
 
Ultrasound & MRI
 
PSA & ultrasound & MRI
 
 
 
For each HDP, summary statistics for the population of patients with all positive tests, in terms of: 
 
Total number biopsied (Section 10.3.5)
 
Total number detected to have clinically insignificant cancer
 
 
 
	Participants biopsied, and who completed the relevant test for the respective analysis 

Imperial Clinical Trials Unit	STATISTICAL ANALYSIS PLAN	PROSTAGRAM
-------------------------------	---------------------------	------------

	(Section 8.1.2), in targeted and non-targeted cores	
	
 
Total number detected to have clinically significant cancer (Section 8.1.1), in targeted and non-targeted cores
 
	
Proportion of men who go onto definitive local or systemic treatment.	Proportion who undergo each treatment: 
 
Active surveillance
 
Watchful waiting
 
Focal treatment
 
Radical prostatectomy
 
Radical radiotherapy
 
ADT
 
	Participants with positive screening results, by each screening test 
Feasibility		

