Sensitivity and specificity analysis will be conducted between screening test results and histology results (reference standard). Histology results will be dichotomised into "clinically significant cancer" and "absence of clinically significant cancer" (repeated for each of the threshold definitions in Section 8.1). The following measures of test accuracy will be reported, along with

Imperial Clinical Trials Unit	STATISTICAL ANALYSIS PLAN	PROSTAGRAM
----------------------------------	---------------------------	------------

their 95% confidence intervals: negative predictive value (NPV), positive predictive value (PPV), sensitivity and specificity. Results will be displayed using graphs for each screening test.

The proportions of false positive results will be reported, with histology as reference. This analysis will be repeated for each of the definitions of false positive results outlined in Section 10.3.8.

For each HDP (see Section 8.3) the proportion of participants with all positive tests, along that pathway, will be reported. For each HDP, we will take the population of participants with all positive tests along each pathway and provide summary statistics. Screen-positive results for MRI are defined by PIRADS cut-off [2] in Section 10.3.1. Similarly, screen-positive results for ultrasound are defined by US cut-off [2] in Section 10.3.2. A “positive” PSA result is defined by a raised PSA level ( $\geq 3.0\text{ng/ml}$ ) (see Section 10.3.3). The summary statistics will be in terms of: the total number of patients who were biopsied (see Section 10.3.5), the total number of patients who were detected to have clinically insignificant cancer in targeted and non-targeted cores, separately, and, the total number of patients who were detected to have clinically significant cancer in targeted and non-targeted cores, separately. This analysis will be limited to the generally accepted definitions for the detection of clinically significant and insignificant cancers (definitions (i) in Sections 8.1.1 & 8.1.2) (7), only.

The proportions of patients, with positive test results by each screening test, who go onto local or systemic treatment for prostate cancer (see Section 10.3.6) will be reported. Positive screening test results will be defined using the PSA cut-off in Section 10.3.3, and both PIRADS and US cut-offs in Sections 10.3.1 & 10.3.2.

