### 11.6.2. Other Test Performance (MRI and US) End Points

**Table 1.2. 1: Number of patients completing the screening tests (MRI, ultrasound and/or PSA)**

	N
All three screening tests: MRI, ultrasound & PSA	xxx
Two screening tests, only: MRI & Ultrasound MRI & PSA Ultrasound & PSA	xxx xxx xxx
One screening test, only: MRI Ultrasound PSA	xxx xxx xxx
Total	xxx

**Table 1.2. 2: Proportion of men with a screen-positive MRI, screen-positive ultrasound and/or raised PSA level**

Screen-positive results	Positive MRI (≥ 3)* (Cut-off [1])		Positive MRI (≥ 4) (Cut-off [2])		Positive ultrasound (≥ 3) (Cut-off [1])	Positive ultrasound (≥ 4) (Cut-off [2])	Raised PSA (≥ 3.0ng/ml)
	Likert	PIRADS	Likert	PIRADS	US	US	PSA
Scoring system	Likert	PIRADS	Likert	PIRADS	US	US	PSA
Proportion – n (%)	xxx (xx%)	xxx (xx%)	xxx (xx%)	xxx (xx%)	xxx (xx%)	xxx (xx%)	xxx (xx%)
95% confidence interval	x.xx to x.xx	x.xx to x.xx	x.xx to x.xx	x.xx to x.xx	x.xx to x.xx	x.xx to x.xx	x.xx to x.xx
Missing from eCRF  – n (%)	xx (xx%)	xx (xx%)	xx (xx%)	xx (xx%)	xx (xx%)	xx (xx%)	xx (xx%)

\*Primary end point.

See Sections 10.3.1, 10.3.2 and 10.3.3 for definitions of thresholds

Proportion who did not undergo the screening test out of the total number of patients recruited

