**Table 1.2. 7: Proportion of men within each value of the discrete PIRADS score (MRI scoring system) and corresponding type of clinical cancer detected**

See Table 1.2. 6, but for discrete values of the PIRADS scoring system.

See Section 8.1 for definitions.

**Table 1.2. 8: Proportion of men within each value of the discrete ultrasound score (US) and corresponding type of clinical cancer detected**

See Table 1.2. 6, but for discrete values of the US scoring system.

See Section 8.1 for definitions.

**Table 1.2. 9: Proportion of men within each PSA level (raised and normal) and corresponding type of clinical cancer detected**

Definition 	Type of clinical cancer	PSA Level	
		Raised ( $\geq 3.0$ ng/ml)	Normal ( $< 3.0$ ng/ml)
i	Clinically significant cancer	xxx (xx%) x.xx to x.xx	xxx (xx%) x.xx to x.xx
	Clinically insignificant cancer	xxx (xx%) x.xx to x.xx	xxx (xx%) x.xx to x.xx
	No cancer	xxx (xx%) x.xx to x.xx	xxx (xx%) x.xx to x.xx
ii	Clinically significant cancer	xxx (xx%) x.xx to x.xx	xxx (xx%) x.xx to x.xx
	Clinically insignificant cancer	xxx (xx%) x.xx to x.xx	xxx (xx%) x.xx to x.xx
	No cancer	xxx (xx%) x.xx to x.xx	xxx (xx%) x.xx to x.xx
iii	Clinically significant cancer	xxx (xx%) x.xx to x.xx	xxx (xx%) x.xx to x.xx
	Clinically insignificant cancer	xxx (xx%) x.xx to x.xx	xxx (xx%) x.xx to x.xx
	No cancer	xxx (xx%) x.xx to x.xx	xxx (xx%) x.xx to x.xx
iv	Clinically significant cancer	xxx (xx%) x.xx to x.xx	xxx (xx%) x.xx to x.xx

	Clinically insignificant cancer	xxx (xx%) x.xx to x.xx	xxx (xx%) x.xx to x.xx
	No cancer	xxx (xx%) x.xx to x.xx	xxx (xx%) x.xx to x.xx
v	Clinically significant cancer	xxx (xx%) x.xx to x.xx	xxx (xx%) x.xx to x.xx
	Clinically insignificant cancer	xxx (xx%) x.xx to x.xx	xxx (xx%) x.xx to x.xx
	No cancer	xxx (xx%) x.xx to x.xx	xxx (xx%) x.xx to x.xx

See Section 8.1 for definitions.

See Section 10.3.3 for definitions.

**Table 1.2. 10: Comparisons of proportions of results between pairs of screening tests (MRI & ultrasound, MRI & PSA and ultrasound & PSA) using McNemar chi square tests**

McNemar's test statistic		MRI		Ultrasound		PSA
		Positive MRI (PIRADS ≥ 3) (Cut-off [1])	Positive MRI (PIRADS ≥ 4) (Cut-off [2])	Positive ultrasound (US ≥ 3) (Cut-off [1])	Positive ultrasound (US ≥ 4) (Cut-off [2])	Raised PSA (≥ 3.0 ng/ml)

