Screen-positive vs screen-negative using definitions in Sections 10.3.1, 10.3.2 and 10.3.3

Clinically significant cancer vs absence of clinically significant cancer. See Section 8.1 for threshold definitions

**Table 1.2. 12: Proportions of false positive results by each screening test (MRI, ultrasound and PSA) with histology (no cancer) as reference**

False positive results (histology as reference)	MRI (PIRADS) 		Ultrasound (US) 		PSA 
	Cut-off [1] ( $\geq 3$ )	Cut-off [2] ( $\geq 4$ )	Cut-off [1] ( $\geq 3$ )	Cut-off [2] ( $\geq 4$ )	Raised ( $\geq 3.0$ ng/ml)
Proportion – n (%)	xxx (xx%)	xxx (xx%)	xxx (xx%)	xxx (xx%)	xxx (xx%)
95% confidence interval	x.xx to x.xx	x.xx to x.xx	x.xx to x.xx	x.xx to x.xx	x.xx to x.xx

False positive results are defined as a screen-positive result when prostate cancer is not present on biopsy (no cancer found on biopsy) (see Section 10.3.8)

See Section 10.3.1, 10.3.2 and 10.3.3

**Table 1.2. 13: Proportions of false positive results by each screening test (MRI, ultrasound and PSA) with histology (no cancer or Gleason 3+3) as reference**

Imperial Clinical Trials Unit	STATISTICAL ANALYSIS PLAN	PROSTAGRAM
----------------------------------	---------------------------	------------

See Table 1.2. 12, but for false positive results, with histology as reference, defined as a screen-positive result when no prostate cancer or Gleason 3+3 is present on biopsy.

False positive results are defined as a screen-positive result when prostate cancer is not present on biopsy or Gleason 3+3 is present on biopsy

See Section 10.3.1, 10.3.2 and 10.3.3

Imperial Clinical Trials Unit	STATISTICAL ANALYSIS PLAN	PROSTAGRAM
-------------------------------	---------------------------	------------

**Table 1.2. 14: Comparison of different testing combinations in terms of biopsy rates, detection of clinically insignificant cancer, in targeted and non-targeted cores, and clinically significant cancer, in targeted and non-targeted cores**

		Hypothetical Diagnostic Pathways 						
		MRI 	Ultrasound 	PSA ( $\geq$ 1.0ng/ml) & MRI 	PSA ( $\geq$ 3.0ng/ml) & MRI 	PSA & Ultrasound 	Ultrasound  & MRI 	PSA & Ultrasound  & MRI 

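### SAP Table 1 limits the pathway comparison to biopsied men, at odds with SAP 11.2.3, and Table 1.2.14 states no denominator, so it gives no biopsy rate per man screened

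*SAP*

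**What the plan says.** The end point (SAP 4.2.1 and 11.1.3) compares testing combinations on biopsy rates and on detection of insignificant and significant cancers. Five places bear on who is counted:

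- **SAP Table 1, pathway row, Population cell:** "Participants biopsied, and who completed the relevant test for the respective analysis".
- **SAP Table 1, same row, Analysis cell:** "For each HDP, summary statistics for the population of patients with all positive tests, in terms of" the total biopsied and the totals with each cancer type.
- **SAP 11.2.3:** "the proportion of participants with all positive tests, along that pathway, will be reported", and then "we will take the population of participants with all positive tests along each pathway and provide summary statistics". No biopsy condition is set, and no denominator is named for the proportion.
- **SAP 9.1:** "Analysis will be carried out for the evaluable population", meaning eligible men with at least one screening test completed. Footnote 1 to Table 1 says each row's population also satisfies this definition.
- **SAP Table 1.2.14:** the title promises biopsy rates and "detection of clinically insignificant cancer, in targeted and non-targeted cores, and clinically significant cancer, in targeted and non-targeted cores". Each cell takes a count, a percentage and an interval. The rows are all screen-positive, biopsied, and the two cancer types by core type. Neither rows nor footnotes give an N or a denominator.

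SAP 10.3.5 defines biopsy rates as a recorded number of patients. Under SAP 8.2 a man goes to biopsy if any one test is positive.

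**The concern.** A biopsy rate needs a denominator that includes men who were not biopsied. The Population cell excludes them. The Analysis cell and 11.2.3 use a different group and then count how many of it were biopsied, which measures uptake among men flagged. Neither gives biopsies generated per man screened, which is what separates a pathway that flags few men from one that flags many.

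The stated purpose (protocol 2.2, objective 5) is to explore which combination or sequence might be the best strategy to take into a definitive study. If the denominator is left open, the percentages and intervals in the table depend on which sentence the analyst follows, and the choice could be made after the results are seen.

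**Working it through.** **1. The possible denominators for the biopsied row**

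- All biopsied men (Population cell read alone): the percentage is the share of all biopsies that fell to men positive on that pathway.
- Biopsied and pathway-positive men (both cells read together): 100% by construction.
- Pathway-positive men (11.2.3): biopsy uptake.
- Men screened: a biopsy rate. No row is explicitly tied to this.

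**2. Reproducing the plan's figures.** From protocol 9.1: raised PSA 0.104, normal PSA 0.896; MRI-positive in raised PSA 0.73; MRI-positive in normal PSA 0.1337 (meta-analysis accuracy) or 0.5975 (PROMIS accuracy).

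- PSA and MRI both positive: 0.104 × 0.73 = 0.07592 (stated 7.59%).
- MRI positive: 0.07592 + 0.896 × 0.1337 = 0.19572 (stated 19.6%), or 0.07592 + 0.896 × 0.5975 = 0.61128 (stated 61.1%).
- n = 1.96² × P(1 − P) / 0.05² = 242.1, rounded up to 243, or 365.2, rounded up to 366. Both match.

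**3. Men biopsied.** With ultrasound ignored and full uptake, these are men positive on PSA or MRI: 0.104 + 0.896 × 0.1337 = 0.22380 (81.9 of 366), or 0.104 + 0.896 × 0.5975 = 0.63936 (234.0 of 366).

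**4. Pathway-positive men under each denominator**

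| Pathway | Of men screened | Of all biopsied men | Of pathway-positive men |
|---|---|---|---|
| PSA ≥3.0 & MRI | 7.6% (27.8 of 366) | 0.07592/0.22380 = 33.9%, or 0.07592/0.63936 = 11.9% | 100% |
| MRI alone | 19.6% (71.6) or 61.1% (223.7) | 0.19572/0.22380 = 87.5%, or 0.61128/0.63936 = 95.6% | 100% |

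The shares of biopsied men are upper limits, because ultrasound-only positives enlarge the denominator. If those add an assumed 20% of men, PSA & MRI falls to 0.07592/0.42380 = 17.9% or 0.07592/0.83936 = 9.0%, and MRI alone to 46.2% or 72.8%.

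**5. Incomplete uptake (assumed 80%, equal across groups).** Over pathway-positive men the biopsied row reads 80% for both pathways. Over biopsied, pathway-positive men it reads 100% for both. Per man screened it is 0.8 × 0.07592 = 6.1% against 0.8 × 0.19572 = 15.7% (or 0.8 × 0.61128 = 48.9%). Restricting to biopsied men also cuts the all-screen-positive count for MRI alone from 71.6 to 57.3, or from 223.7 to 178.9.

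**6. Does the denominator affect ranking on cancer?** Men positive on PSA & MRI are a subset of men positive on MRI, so per man screened MRI alone cannot detect fewer cancers. Per pathway-positive man the figure is a positive predictive value. The protocol's 2×2 tables give that value for MRI-positive men with normal PSA: 1.63/13.37 = 12.2%, or 2.05/59.75 = 3.4%. The value for MRI alone is a weighted average of this and the value in raised-PSA, MRI-positive men. So PSA & MRI ranks above MRI alone on this measure whenever the raised-PSA value exceeds 12.2% or 3.4%. The documents do not give the raised-PSA value.

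**The case against.** The best defence is that SAP 10.3.5 defines biopsy rates as a number, and that the Analysis cell and 11.2.3 ask for totals. The totals of men biopsied and of cancers are the same from either starting population. Table 1.2.1 gives completer counts for every combination of tests, so a reader could derive per-man rates for each column. All of that stands. It does not settle the matter, because Table 1.2.14 also asks for a percentage and an interval in every cell and the plan does not say of what. Section 9.1 does not supply the answer either: footnote 1 makes it an added condition, so the biopsied restriction remains.

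It is also fair that the two cells of the Table 1 row should be read together. A reader might infer that an analyst following Table 1 and one following 11.2.3 would rank pathways in opposite order on significant cancer. The documents do not support that. Read together, the row means biopsied men within the pathway-positive group. At full uptake this is the pathway-positive group itself, and the cancer percentages agree. The ranking contrast in the working is between per-man and per-positive-man figures, not between those two places in the SAP.

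A reader might also infer that PSA alone goes unreported. It does not: raised PSA appears in Tables 1.2.2, 1.2.9, 1.2.11 to 1.2.13 and 1.2.15. It is absent only from the written pathway list and from the columns of Table 1.2.14. Figure 1, which draws the pathways, is not shown in the text available.

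**Conclusion.** The point holds. The Population cell does not fit an end point on biopsy rates, it conflicts with the Analysis cell beside it and with 11.2.3, and Table 1.2.14 has no denominator. As written, the biopsied percentage is either 100% by construction, or uptake, or a share of all biopsies. A pathway flagging 7.6% of men screened and one flagging 19.6% or 61.1% can look identical in that row.

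The figures show scale only. They rest on MRI ≥3 rates, because the pathways use PIRADS ≥4 and the documents give no rate for that threshold. They also ignore ultrasound unless stated and use assumed uptake.

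No cancer detection rates for the two pathways are offered. They depend on significant-cancer prevalence in men with raised PSA, which the documents do not give. Nor can it be backed out credibly: the protocol's assumption of equal MRI accuracy in both PSA groups, combined with 73% MRI-positive, implies a prevalence of (0.73 − 0.12)/(0.74 − 0.12) = 98% or (0.73 − 0.59)/(0.93 − 0.59) = 41%.

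The comparison is descriptive. The primary end point and the sample size do not depend on it.

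**What to change.** - In SAP Table 1, replace the Population cell of the pathway row with evaluable men who completed PSA, MRI and ultrasound, as one common set for every column. Align 11.2.3 with it.
- Add a sensitivity version using all men whose pathway result is known. For example, a man with PSA below 3.0 and no MRI is negative on PSA ≥3.0 & MRI.
- In Table 1.2.14, state the denominator. Report pathway-positive, biopsied, and significant and insignificant cancers per man in that set.
- Show biopsy uptake (biopsied / pathway-positive) as its own labelled row and, if wanted, cancers per pathway-positive man as another.
- Optional: add a column for PSA ≥3.0 ng/ml alone as comparator, since MRI and ultrasound each have one.

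The cost is SAP wording, one or two table rows and possibly one column, all from data already collected. The downside is a larger table and a slightly smaller common set. The loss should be small, since inability to conduct a test is a withdrawal criterion (SAP 5.4), and the sensitivity version covers it.

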6.4 Prostate USS

Participants will be offered to undergo an ultrasound prior to MRI. The technique for image acquisition and reporting will be standardised in a Standard Operating Procedure (SOP MP-USS). Participants who have identified prostate lesions on ultrasound scored as 3 or greater by the relevant scoring system will be offered a prostate biopsy.

PROSTAGRAM	Protocol no: 18HH4595	Sponsor: Imperial College London	V 1.01MAY2019
-------------------	---------------------------------	---	----------------------

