7.8 Expected Adverse Events Associated with MRI

The following Adverse Events are associated with MRI:

- Claustrophobia
- Anxiety/Stress
- Discomfort

Note: No contrast agent is used in the study prostate MRI protocol

The MRI is a non-contrast scan and equipped with monitoring methods that allow conversation with the participants and identification of any anxiety or discomfort. A detailed history for absolute and relative contraindications for a non-contrast MRI will be taken as set out in MRI SOP.

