#### 11.1.4. Feasibility End Point

- Assess the acceptability of each diagnostic test measured with EBQ, PBQ, and time taken to complete each screening test.

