Assess the acceptability of each diagnostic test measured with EBQ, PBQ and time taken to complete each screening test	
 
EBQ and PBQ Questionnaires (see Appendix 1 for details):             
 
Summary statistics for overall scores for EBQ and PBQ, for each screening test                 
 
Paired t-tests comparing mean overall scores between pairs of screening tests (MRI & PSA, MRI & ultrasound, ultrasound & PSA), for EBQ and PBQ separately
 
Paired t-tests comparing mean difference between pre- and post-screening test scores, for each screening test
 
 
 
Proportions within each value of the Likert score, for each EBQ component, for each screening test (Appendix 1)
 
Mean score for each EBQ component, for each screening test                 
 
Paired t-tests comparing mean component scores between pairs of screening tests (MRI & PSA, MRI & ultrasound, ultrasound & PSA)
 
 
 
Proportions within each value of the Likert score, for each PBQ component, for each screening test (Appendix 1)
 
Mean score for each PBQ component, for each screening test                 
 
Paired t-tests comparing mean component scores between pairs of screening tests (MRI & PSA, MRI & ultrasound, ultrasound & PSA)
 
 
 
 
 
	Participants who completed the relevant test for the respective analyses   For the paired tests, participants who completed both tests in each pair

Imperial Clinical Trials Unit	STATISTICAL ANALYSIS PLAN	PROSTAGRAM
-------------------------------	---------------------------	------------

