#### 20.1.3. EBQ and PBQ

The Expected Burden Questionnaire (EBQ) and Perceived Burden Questionnaire (PBQ) have been developed for use in bowel cancer screening. It has been used in studies investigating the acceptance of CT Colonography/FOBT (10) and has been adapted for the tests used in this study.

EBQ is comprised of four questions addressing the expected extent of embarrassment, pain, burden and anxiety caused by each test. This is followed up by a question summarising which test the patient expects to prefer. The EBQ is completed at visit 1, before the screening tests. The

Imperial Clinical Trials Unit	STATISTICAL ANALYSIS PLAN	PROSTAGRAM
-------------------------------	---------------------------	------------

responses to the first four questions are coded as a 5-point Likert score, 1 = not at all, 2 = slightly, 3 = somewhat, 4 = rather and 5 = extremely (14). Each question, representing each component, will be reported separately. An overall burden score will also be calculated for each screening test by summing the response scores to the first four questions. Lower overall scores represent lower expected overall burden for that particular screening test.

Similarly, PBQ is comprised of five questions addressing the embarrassment, pain, burden and anxiety experienced from each test, and how likely the patient is to have the test again, if recommended. This is followed up by a question summarising which test the patient preferred. The PBQ is completed at visit 1, after each screening test. The responses to the first five questions will be coded as 1 = not at all, 2 = slightly, 3 = somewhat, 4 = rather and 5 = extremely (14). Each question, representing each component, will be reported separately. An overall burden score will be calculated for each screening test by summing the response scores to the first four questions, excluding the question relating to repeat test recommendation. Lower overall scores represent lower perceived overall burden for that particular screening test.

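### SAP Table 1 drops expected-burden (EBQ) answers from men who did not go on to complete a test, although the EBQ is answered beforehand and needs no completed test

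*SAP*

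**What the plan says.** The only feasibility end point in the primary paper (SAP 11.1.4) is to "Assess the acceptability of each diagnostic test measured with EBQ, PBQ, and time taken to complete each screening test". One population cell in the Feasibility row of SAP Table 1 governs the whole end point. It reads "Participants who completed the relevant test for the respective analyses", followed by "For the paired tests, participants who completed both tests in each pair". The cell therefore covers EBQ and PBQ summaries, between-test t-tests, EBQ-to-PBQ change, preference and time. Neither *completed* nor, for the single preference question across three tests, *the relevant test* is defined.

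On timing, SAP 20.1.3 states "The EBQ is completed at visit 1, before the screening tests" and "The PBQ is completed at visit 1, after each screening test". Protocol 6.5 likewise puts the EBQ before each test and the PBQ after it. SAP 9.1 defines the evaluable population as eligible men with at least one of MRI, ultrasound or PSA done, so a man who misses an imaging test is not removed by that definition. Protocol 8.4.1 allows data collected up to withdrawal to be used if anonymised.

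**The concern.** Whether a man completes a test can depend on how acceptable he finds it. Protocol 6.4 says "Participants will be offered to undergo an ultrasound prior to MRI", which leaves room to decline, and Protocol 7.8 lists claustrophobia, anxiety and discomfort as expected events of MRI. Restricting to completers can therefore select men on something close to the quantity being measured.

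For the EBQ the restriction has no statistical purpose. Expected burden exists whether or not the test follows. A man who expected MRI to be hard and then did not have it leaves the MRI summaries and both the MRI–PSA and MRI–ultrasound comparisons, although he answered the questions.

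At stake are the EBQ means, the EBQ between-test differences and expected preference. These feed the judgement of whether imaging is acceptable as a screening test. The primary end point, the screen-positive MRI proportion, is not affected.

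**Working it through.** **1. Which analyses need a completed test?**

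- *EBQ scores, EBQ between-test t-tests, expected preference:* answered beforehand, so completion is not needed. The restriction is avoidable.
- *PBQ scores and final preference:* these concern experience of the tests. A man who never started a test has no experience of it. One who started and stopped does, and may have a PBQ.
- *EBQ-to-PBQ change and time taken:* these need both scores, or a finished procedure. The restriction is inherent.

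**2. Plan figures.** The plan states no figure for acceptability or for non-completion by test. Its sample size supplies only the number of men: 1.96² × 0.611 × 0.389 / 0.05² = 365.2, stated as 366. Dividing 365.2 by 0.9 gives 405.8, stated as 406. Both figures reproduce.

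**3. Scale.** The overall EBQ score sums four items scored 1 to 5, so it runs from 4 to 20 (SAP 20.1.3). The largest possible gap is 16.

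**4. Formula.** Let f be the share with EBQ answers who did not complete the test, and g the excess of their mean expected burden over the completers' mean. The mean in all men is (1 − f) × completer mean + f × (completer mean + g) = completer mean + f × g. The completers-only mean is therefore too low by f × g. For a between-test difference the same formula holds, with f the share lacking either test and g the excess of the difference in those men over that in completers.

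**5. Assumed range.** Neither f nor g is in the documents. The 10% is the plan's overall dropout allowance, borrowed as an upper value. It is not a stated non-completion rate.

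| f | men out of 406 | bias if g = 4 | bias if g = 8 |
|---|---|---|---|
| 2% | 8.1 | 0.08 | 0.16 |
| 5% | 20.3 | 0.20 | 0.40 |
| 10% | 40.6 | 0.40 | 0.80 |

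The arithmetic ceiling at f = 10% is 0.10 × 16 = 1.60 points. At f = 0 the bias is nil.

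**6. Against sampling error.** The 95% half-width is 1.96 × SD / √n. At n = 366 and an assumed SD of 2, 3 or 4 points it is 0.20, 0.31 or 0.41. With g = 4, the bias is well inside this at f = 2%, at most equal to it at f = 5%, and similar or larger at f = 10%.

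**The case against.** The strongest reply is that most of the restriction is unavoidable and that the group concerned is small by design. Perceived burden, change from expected to perceived burden, and time to completion cannot be measured in men who did not have the test. Claustrophobia and any potential MRI contraindication are exclusions. Men must be fit for all procedures, receive the information sheet at least 24 hours ahead and give written consent. That ultrasound is offered does not show that refusal is common.

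Non-completion is also not hidden. SAP Tables 1.2.1 and 1.2.2 count it, and SAP 12 describes men with missing data and gives reasons for loss to follow-up. Table 1.5.2 tabulates claustrophobia, anxiety and discomfort. The PBQ's repeat-test item is reported per test. Retention is a defined end point, and a separate feasibility paper is planned.

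All of this stands, and it narrows the point. It does not justify discarding EBQ answers already given. None of the listed outputs puts non-completion, separated into declining and stopping, beside the burden results.

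A reader might go further and infer that the PBQ and final-preference results are shown to be biased in favour of imaging, or that a man whose scan was stopped has no burden score. The documents do not support either. The PBQ follows each test, *completed* is undefined, and nothing states how a stopped test is handled.

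**Conclusion.** The point holds for the EBQ summaries, the EBQ between-test comparisons and expected preference: the population rule drops valid data for no analytical reason. The direction rests on the plausible but undocumented assumption that men who declined or could not complete a test expected more burden from it. Under that assumption, mean expected burden is understated and between-test differences shift in favour of the less-completed test.

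The size cannot be determined from the plan. At the assumed g of 4 points it is 0.08 to 0.40 points for f of 2% to 10%, and given the exclusions it may sit at or below the low end. A reader might infer that the bias outweighs the margin of error. That needs an f, g and SD chosen for the purpose, and the plan supplies none of them.

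The PBQ, EBQ-to-PBQ change and time results are legitimate, but they describe burden among men who had the test and should be labelled so. This is an inexpensive improvement to a secondary end point.

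**What to change.** 1. In SAP Table 1 and SAP 11.2.4, set the population for EBQ scores, EBQ between-test comparisons and expected preference to all evaluable men with EBQ responses for the test or tests concerned, whether or not the test was later completed. Apply the missing-item rule in SAP 12.1 per questionnaire and per test, so that an absent PBQ does not remove a man's EBQ.
2. In the PBQ summaries, include any man who started a test and has a PBQ for it, and label the results as burden among men who had the test. This should use PBQs that exist. Inability to conduct a test is a withdrawal criterion, and Protocol 8.4.1 stops further case report forms after complete withdrawal, so requiring a PBQ after every stopped test might need a protocol change.
3. Beside the EBQ and PBQ tables, report for each test the number and percentage who declined, stopped early or completed, with reasons.

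A sensitivity analysis giving unfavourable scores to men who stopped for intolerance is optional. It would assign burdens, such as pain, that a given man may not have had.

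The cost is SAP wording, a few table rows, and slightly different Ns between the EBQ and PBQ tables. Sample size and visits do not change.
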